6.2.1.2 Primary Efficacy Variable: Sensitivity Analysis

As a sensitivity analysis, the number of primary composite events will also be analyzed using a negative binomial regression model including stratification factors and treatment group as covariates and log follow-up time as an offset parameter.

As a sensitivity analysis, plots and summaries of the mean cumulative function for the primary endpoint will be derived based on a competing-risk approach (Ghosh and Lin, 2000) and cumulative incidence function for the competing event of non-CV death (Aalen and Johansen, 1978) will be presented by treatment group. The following SAS Code illustrates the program for the mean cumulative function for the primary endpoint:

```
PROC PHREG DATA=primary;  
  MODEL (time_start, time_rec)*event(0)= / eventcode=1;  
  STRATA treat;  
  ID patid;  
  BASELINE OUT=mcfdat CIF=cif LOWERCIF=lcif UPPERCIF=ucif /  
    SEED=999;  
RUN;  
  
DATA mcfdat;  
  SET mcfdat;  
  mcf = -log(1-cif)  
  lmcf = -log(1-lcif)
```

```
ucif = -log(1-ucif)  
RUN;
```

primary is the input dataset, time_start is the previous event stop time and time_rec is the current event stop time, the event variable event (0 for censored, 1 for primary event, and 2 for competing event) and patid is the participant ID and treat is the treatment group identifier.

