Participants will be randomized in a 1:1 ratio to either finerenone or placebo. The study is designed to be able to show an effect on the primary endpoint with a power of 90% at an alpha level of 5%. It was originally anticipated that 5500 participants will be randomized and approximately 6900 will be screened (screening failure rate of approximately 20%). A total of approximately 2375 total (first and recurrent) primary composite events are targeted. Due to blinded event rates being lower than those assumed in the sample size calculation, the planned number of randomized participants was increased to approximately 6000. The target number of primary composite events was not changed.

The anticipated duration of the study will be approximately 42 months, with a recruitment period of 24 months. However, as an event-driven study, the actual length of the study will depend on the observed event rates, the participant recruitment rate, and the length of the recruitment period.

Enrolment in the trial may be capped based on the proportion of patients in certain LVEF categories, in each NYHA class, with/without atrial fibrillation, and by geographic region, among other variables, to ensure recruitment of a representative study population.

The randomization will be stratified by country/region and baseline LVEF ($<60\%$, $\geq 60\%$).

Since all randomized participants (excluding those with critical GCP violations) belong to the Full Analysis Set (FAS) on which the efficacy analyses are based, it is important to avoid randomization of non-eligible patients into the study.

[figure not shown]
The general study design as applied to this study is shown in Figure 3-1. There is a screening period, a double-blind treatment period and a safety follow-up period. Patients prematurely terminating from the study and up to the primary study completion will be asked to attend scheduled visits to collect efficacy data.

Statistical Analysis Plan

Protocol No.: BAY 94-8862/20103

Page: 10 of 53

Figure 3-1: Study design

Screening Visit

After providing written informed consent, a Screening Visit to confirm the participant's eligibility will take place prior to randomization. The Screening Visit may take place on the same day as randomization (Visit 1).

Treatment Period

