The primary analysis method has been investigated with extensive simulation studies and it has been confirmed that it keeps the alpha level and has good operating characteristics across a range of plausible scenarios. A small adjustment will be made to the nominal significance level and the critical value at the final analysis to take into account the interim analysis (see Section 4.7 for details). No adjustment to the sample size calculation is done for this.

The SAS code below illustrates the program for the Anderson-Gill model:

```
PROC PHREG DATA=primary COVS (aggregate);  
  MODEL (time_start, time_rec)*status(0)=treat/ties=efron rl;  
  ID patid;
```

```
STRATA {stratum};  
RUN;
```

primary is the input dataset, time_start is the previous event stop time and time_rec is the current event stop time, the censoring variable status (0 for censored and 1 for event) should take the value 1 if the last event is a CV death and 0 if it is censored for a non-CV death or at the end of study for the given patient; patid is the participant ID and treat is the treatment group identifier.

If a participant experiences an HF event and subsequently dies for a cardiovascular reason, this will be considered as two separate events for the primary analysis unless the participant dies on the same calendar day as the HF event (both events would still be considered for the analyses of the separate components). If a participant is hospitalized for HF shortly after an urgent HF visit, this will be considered as two separate events for the primary analysis unless they occur on the same calendar day.

Additionally, plots and summaries of the mean cumulative function for the primary endpoint (Nelsen-Aalen estimate) will be presented by treatment group.

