6.2.1.3 Primary Efficacy Variable: Supportive Analysis of CV death component

As part of the primary analysis, a separate estimate of the treatment effect for CV death as one of the components of the primary endpoint will be obtained. The second component of total HF events will be a secondary endpoint and analyzed as described in Section 6.2.2.1.

The main cause-specific treatment effect estimate for CV death will be derived from a stratified Cox proportional hazards model for time to CV death and the main p-value from a stratified log-rank test. A cause-specific treatment effect estimate for the censoring event of non-CV death will also be calculated using a stratified Cox proportional hazards model and presented with associated 95% confidence interval. The cumulative incidence functions for time to CV death and time to non-CV death will also be calculated using Aalen-Johansen estimates.

Note that the study is not powered to show an effect on CV death alone. While this is the case, a sufficient number of deaths are expected so that an excess risk in mortality can be excluded. Under the assumptions of the sample size determination, approximately 535 CV deaths and approximately 775 all-cause deaths are expected to occur in the study. Even though no formal statistical tests for exclusion of an increased risk will be performed, these expected event counts would result in a relatively high power to exclude increased hazard ratios (HRs) on ACM. Table 6-1 provides the respective power values to exclude HRs above 1.15 and 1.25 under different assumed values for the true HR on CV death and assuming no treatment effect on non-CV deaths ($HR_{NonCVD}=1.0$). Similar to the primary endpoint, a treatment policy strategy is used for treatment discontinuation. With exclusion of a certain HR value it is meant that the upper limit of a 95% CI is below the value.

Table 6-1: Power to exclude increased HR on ACM under different assumed treatment effects on CV death

| True HR_{CVD} | Exclude $HR_{ACM}>1.15$ | Exclude $HR_{ACM}>1.25$ |
|-----------------|-------------------------|-------------------------|
| 0.8 | 94% | >99% |
| 0.9 | 78% | 97% |
| 1.0 | 52% | 88% |

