6.2.2.2 Secondary Efficacy Variables: Sensitivity Analysis

As a sensitivity analysis for the total HF events endpoint, a joint frailty model (Rogers et al., 2016) with constant baseline hazard for CV death and constant baseline intensity for HF events will be fitted including effects for treatment group, pooled region for stratified analyses

and baseline LVEF ($<60\%$, $\geq 60\%$). A gamma frailty distribution will be assumed. This model gives a treatment effect on total HF events which is adjusted for a potential treatment effect on CV death. An effect on CV death might otherwise dilute the effect seen on the hospitalizations, i.e. an effective treatment will prevent CV deaths especially in the more severely ill participants, which then potentially results in many hospitalizations.

The joint frailty model can sometimes have convergence issues (Toenges & Jahn-Eimermacher, 2020); additionally, estimates obtained from the model have sometimes been observed as unstable (e.g., large differences with changes in starting values and/or ordering of covariates in the model). Should such problems be encountered, a simpler model including only treatment group as a fixed effect will be used instead. The joint frailty model additionally produces an estimate for CV death; however, this will be considered only supportive for the analysis of this component and instead the main analysis for the CV death component is described under the primary efficacy variable in Section 6.2.1.2.

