Frequency tables will be generated for the number and percentage of patients with a relative decrease in eGFR of $\geq 25\%$, $\geq 30\%$, $\geq 40\%$, $\geq 50\%$ and $\geq 57\%$ from baseline. The analysis will be performed for each visit and for any time post-baseline.

The rate of change of eGFR will be compared between the finerenone and the placebo group by estimating the total eGFR slope using available assessments from baseline to planned end of the treatment period. It is assumed that changes in the mean response can be expressed in terms of a linear trend, and the treatment effect can be expressed in terms of the difference in slope between finerenone and placebo. For the analysis of the total slope, the serial change in eGFR will be modeled using a two-slope linear spline mixed-effects model in which a fixed change point will be defined to separate acute and chronic eGFR slope at Month 3 (Section 2.1 of Vonesh et al. 2019). In addition to fixed effects for the treatment, time (continuous) and treatment by time interaction, the model will include fixed effects for the stratification factors and random effects for the intercept, acute slope (baseline to Month 3), and chronic slope (Month 3 to planned end of treatment period). An unstructured covariance will be used to model the between-participant errors. Within-participant errors are assumed to be homogenous. Linear contrasts will be constructed to estimate the acute, chronic, and total slope in eGFR. LS means and differences of the acute, chronic and total eGFR slope for finerenone and placebo group will be provided with 95% confidence intervals (and corresponding p-values for the differences).

DAOH will be summarized descriptively by treatment group; the number and percentage of DAOH with respect to total potential follow-up time will be provided alongside the number and percentage of days dead and days in hospital, including breakdown into type of death. These analyses will be performed overall and separately by the stratification factors (pooled region for stratified analyses and LVEF).

DAOH will be analyzed by an ANCOVA model including potential follow-up time, treatment group, and stratification factors as fixed effects. Potential follow-up time is defined as the time from randomization up to end of study or lost to follow-up or withdrawal date, in case the patient did not complete the study.

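### Is the competing-risk mean cumulative function in SAP 6.2.1.2 deficient because it makes only non-CV death terminal?

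*SAP*

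**What the plan says.** The primary estimand (SAP 2; Protocol 3 and 9.1) counts CV death as an outcome and then as censoring, and treats non-CV death as censoring. SAP 2 and Protocol 9.1 give the reason: building into the model that no HF event can follow death would favour an arm with more early deaths.

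SAP 6.2.1.1 codes the primary model accordingly. The status variable "should take the value 1 if the last event is a CV death and 0 if it is censored for a non-CV death". The curve shown with the primary analysis follows the same rule: the "mean cumulative function for the primary endpoint (Nelsen-Aalen estimate) will be presented by treatment group". The same section plans the number and incidence rate of primary events and of non-CV deaths by arm.

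SAP 6.2.1.2 adds a Ghosh-Lin curve as a sensitivity display, together with the "cumulative incidence function for the competing event of non-CV death". Its code note reads "the event variable event (0 for censored, 1 for primary event, and 2 for competing event" and does not define code 2 further. Reading code 2 as non-CV death only is an inference from that sentence, from the status rule in 6.2.1.1 and from Protocol 9.1. It is the likelier reading and is used below.

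Death is also examined elsewhere:
- SAP 6.2.1.3: "The cumulative incidence functions for time to CV death and time to non-CV death will also be calculated using Aalen-Johansen estimates".
- SAP 6.2.1.5: the primary model repeated for total HF events and all-cause mortality.
- SAP 6.2.2.2: a joint frailty model for total HF events. "This model gives a treatment effect on total HF events which is adjusted for a potential treatment effect on CV death".
- SAP 6.2.3: days alive and out of hospital, with "the number and percentage of days dead and days in hospital".

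**The concern.** A mean cumulative function that carries the Ghosh-Lin reference and a competing-risk label suggests that death has been fully accounted for. Here it has been only for the minority of deaths that are non-CV. After a CV death the method behaves as though the patient could have had further events, so the curve lies above the mean number of events that randomised patients actually have. The excess is larger in the arm with more events, so the displayed difference between arms is larger as well.

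No other planned curve fills the gap. The remaining mean cumulative functions are Nelson-Aalen, and the Aalen-Johansen curves cover death or first events only. Anyone who read absolute events prevented per 100 patients from either planned curve would overstate the benefit relative to a count in which every death ends follow-up.

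**Working it through.** **Inputs** (Protocol 9.2): placebo HF rate 0.0182, CV-death hazard 0.005125 and non-CV-death hazard 0.0016 per month; gamma frailty with variance 5.0 shared by HF events and CV death; HF rate ratio 0.75; CV-death hazard ratio 0.80; 5% discontinuation per year with return to placebo risk. Assumed, because not stated: frailty mean 1, discontinuation hazard −ln(0.95)/12 per month, follow-up uniform over 18 to 42 months.

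**Formulas.** Let r(t) be the composite event rate among patients alive at t, S_n(t) = exp(−0.0016t) survival from non-CV death, and S_c(t) survival from CV death. For placebo, S_c(t) = (1 + 0.025625t)^(−1/5) and r(t) = 0.023325/(1 + 0.025625t), where 0.025625 = 5 × 0.005125 and 0.023325 = 0.0182 + 0.005125. For finerenone the same quantities are averaged over the time of discontinuation.
- Nelson-Aalen: ∫ r dt
- As coded: ∫ S_n r dt
- All deaths terminal: ∫ S_n S_c r dt

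**Planning figures first.** The model gives 2376 total events (stated 2375), 1310 first events (1310), 533 CV deaths (535) and 776 deaths (775), so it is the plan's own model.

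**Hand check**, placebo Nelson-Aalen at month 36: (0.023325/0.025625) × ln(1 + 0.025625 × 36) = 0.9102 × 0.6536 = 0.595, or 59.5 per 100.

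**Month 36, per 100 patients:**

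| Curve | Placebo | Finerenone | Difference | Ratio |
|---|---|---|---|---|
| Nelson-Aalen | 59.50 | 48.70 | 10.80 | 0.818 |
| As coded | 58.00 | 47.44 | 10.55 | 0.818 |
| All deaths terminal | 54.40 | 44.90 | 9.50 | 0.825 |

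The gap between the coded and all-deaths-terminal differences is 10.55 − 9.50 = 1.05.

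**Dependence on time.** With follow-up uniform over 18 to 42 months, only (42 − 36)/24 = 25% of patients can be followed beyond month 36.

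| Month | As coded | All deaths terminal | Gap |
|---|---|---|---|
| 12 | 5.18 | 4.96 | 0.22 |
| 24 | 8.41 | 7.78 | 0.63 |
| 30 (mean follow-up) | 9.58 | 8.74 | 0.84 |
| 36 | 10.55 | 9.50 | 1.05 |

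**Dependence on rates.** SAP 3 reports a larger sample "Due to blinded event rates being lower than those assumed in the sample size calculation" but gives no figure. If all rates are 20% lower (assumption), the month-36 differences are 9.40, 9.23 and 8.44, so the gap is 9.23 − 8.44 = 0.79. At planned rates the gap is about 0.85 with a CV-death hazard ratio of 0.9 and 0.64 with 1.0.

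**Against sampling error.** In simulation at 5500 patients and planned rates, the coded difference has a standard deviation of 3.63 per 100, and 1.05/3.63 = 0.29. At 6000 patients, with rates 20% lower and follow-up lengthened to reach the event target, 0.79/2.94 = 0.27.

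**What the planned counts already give.** A patient who has died adds no further events to the count in SAP 6.2.1.1. Events divided by patients randomised is therefore the all-deaths-terminal curve averaged over actual follow-up, apart from dropout. Under the planning model this is 47.51 per 100 on placebo and 38.91 on finerenone, a difference of 8.60. With 2750 patients per arm, 47.51 × 27.5 + 38.91 × 27.5 = 1306.5 + 1070.0, or about 2376 events, which agrees with the plan's total.

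**The case for a change.** The best case for acting runs as follows. The competing-risk label promises more than the curve delivers. Under the planning model both planned curves exceed the all-deaths-terminal difference in the same direction: Nelson-Aalen by 14% (10.80/9.50) and the coded curve by 11% (10.55/9.50). The coded curve closes only 0.25 of the 1.30 between them. The gap is systematic, so a larger trial does not remove it, and it persists with no effect on CV death. One extra curve fixed before unblinding would be cheap.

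The arithmetic stands. So does the observation that no planned curve over time treats every death as terminal, and that code 2 could have been defined more plainly.

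The rest does not amount to a defect. It cannot be said that no planned output carries the quantity, because the event counts by arm do; only its course over time is missing. The SAP does not offer the coded curve as a test of treating CV death as censoring. The curve that fits the estimand in full is the Nelson-Aalen one in 6.2.1.1. The 6.2.1.2 curve departs from the estimand on non-CV death alone, which is a legitimate job for a sensitivity display. The extra curve would also have the very property that SAP 2 and Protocol 9.1 argue against: it lowers the count in the arm with more deaths. Preferring it as a supplement is a matter of taste, and harm would require someone to make an unplanned absolute-benefit statement from the wrong output.

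**Conclusion.** The concern does not hold. SAP 6.2.1.2 keeps the estimand's handling of CV death, and that handling is disclosed and justified. The curve is descriptive: the primary rate ratio, its test, the stopping rules and the secondary testing sequence do not use it. The contrast with all deaths terminal can be read from planned counts as an average over follow-up (8.60 per 100 under the planning model), and mortality is shown separately by cause.

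The gap at issue is 0.22 per 100 at month 12, rising to 1.05 at month 36, under 0.3 standard deviations of the estimated difference at that point. The ratio of the curves moves from 0.818 to 0.825. These figures rest on the Protocol 9.2 model with frailty mean 1, the stated form of discontinuation, uniform follow-up over 18 to 42 months, and code 2 meaning non-CV death only. Lower event rates shrink the gap. No change to the plan is needed.

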6.2.1.3 Primary Efficacy Variable: Supportive Analysis of CV death component

As part of the primary analysis, a separate estimate of the treatment effect for CV death as one of the components of the primary endpoint will be obtained. The second component of total HF events will be a secondary endpoint and analyzed as described in Section 6.2.2.1.

The main cause-specific treatment effect estimate for CV death will be derived from a stratified Cox proportional hazards model for time to CV death and the main p-value from a stratified log-rank test. A cause-specific treatment effect estimate for the censoring event of non-CV death will also be calculated using a stratified Cox proportional hazards model and presented with associated 95% confidence interval. The cumulative incidence functions for time to CV death and time to non-CV death will also be calculated using Aalen-Johansen estimates.

Note that the study is not powered to show an effect on CV death alone. While this is the case, a sufficient number of deaths are expected so that an excess risk in mortality can be excluded. Under the assumptions of the sample size determination, approximately 535 CV deaths and approximately 775 all-cause deaths are expected to occur in the study. Even though no formal statistical tests for exclusion of an increased risk will be performed, these expected event counts would result in a relatively high power to exclude increased hazard ratios (HRs) on ACM. Table 6-1 provides the respective power values to exclude HRs above 1.15 and 1.25 under different assumed values for the true HR on CV death and assuming no treatment effect on non-CV deaths ($HR_{NonCVD}=1.0$). Similar to the primary endpoint, a treatment policy strategy is used for treatment discontinuation. With exclusion of a certain HR value it is meant that the upper limit of a 95% CI is below the value.

Table 6-1: Power to exclude increased HR on ACM under different assumed treatment effects on CV death

| True HR_{CVD} | Exclude $HR_{ACM}>1.15$ | Exclude $HR_{ACM}>1.25$ |
|-----------------|-------------------------|-------------------------|
| 0.8 | 94% | >99% |
| 0.9 | 78% | 97% |
| 1.0 | 52% | 88% |

6.2.1.4 Primary Efficacy Variable: Supportive Analysis of Time-to first event of Composite Endpoint

As supportive analysis, stratified Cox proportional hazard regression analysis will be performed for the time to first composite of HF event or CV death and a plot of Aalen-Johansen estimates of the cumulative incidence function will be provided.

6.2.1.5 Primary Efficacy Variable: Other Supportive Analyses

A supportive analysis of the primary endpoint will exclude urgent HF visits and consider only CV deaths and HHFs as events. Also, an additional analysis of the primary endpoint will restrict CV deaths to HF-related events and thus will consider HF events and CV deaths due to HF. These analyses will both be performed for total (first and recurrent) events and for first events only.

A total-time approach considering times from randomization to the onset of first, second, third composite event using a Wei, Lin, and Weissfeld (WLW, 1989) model will be applied. This model enables analysis of the cumulative effect on the primary endpoint from randomization (i.e. the effect on second event includes the effect on the first, and the effect on third event includes the effects on the first and second). The corresponding individual HRs with 95% CIs comparing treatment groups on the first, second, and third event will be presented.

In addition, a conditional gap-time model according to Prentice, Williams and Peterson (PWP, 1981) will be applied to obtain HR estimates with 95% CIs for the time from first to second and from second to third event (note that this gives a non-randomized comparison). Both models will employ robust standard errors and include the stratification factors and treatment group as fixed effects. Both WLW and PWP approaches are known to have limitations and hence are strictly only performed as supplemental analyses since they aim at describing different aspects of recurrent events.

An “on-treatment” analysis will be performed, including only events occurring up to 30 days after treatment discontinuation. This analysis will be performed in the SAF instead of the FAS.

In addition, table and figure of risk ratios and respective confidence intervals will be provided for the primary efficacy endpoint with patients being censored sequentially at each study day similar to figure 3 in Packer et al. (2021). The first day where the upper CI of the RR is below 1 and stays below for the remainder will be marked.

The primary analysis for the primary endpoint will also be repeated for the “Total HF events and ACM” endpoint.

In addition, the primary analysis will also be repeated where patients are included with only up to a maximum of 4 composite events, to examine the impact of patients with a large number of events. For this analysis, patients who experienced 4 or more events will be censored at the time of their 4th event.

An additional analysis of the primary endpoint will include a time-dependent covariate for SGLT-2 inhibitor use.

